Protocol Amendment 1 Final

Visit / Contact	Screening	V1	C1	V2 ¹	Monthly contacts until delivery ⁶	V3	V4	C2	Safety Visit - Event-driven	RSV-associated MA-RTI Visit - Event-driven ⁷	Notes
Timepoint	D (-28) – D 1	D1 (24 ^{0/7} - 36 ^{0/7} weeks of gestation)	D8	D31		Delivery	D43 Post-delivery	D181 Post-delivery			For monthly contacts: Section 8.4.2.1 Additional contacts and/or visits can be made between Visit-2 and the Delivery visit if deemed necessary.
the epidemiological COVID-19 situation) (Day 1 post-study intervention to 180 days post-delivery)											
MA-RTIs (Day 1 post-study intervention to 180 days post-delivery) ⁷		O ⁵	O ⁵	O ⁵	O ⁵	O ⁵	O ⁵	O ⁵		•	Sections 8.3.1, 8.3.3, 8.4 and 10.3.8 MA-RTIs for the maternal participants will no longer be performed.
SAEs, (S)AEs leading to study withdrawal, MAEs (Day 1 post-study intervention to 180 days post-delivery)		•	•	•	•	•	•	•	•	•	Sections 7.2, 8.3.1 and 10.3.8
SAEs related to study participation (Screening to Day 1 pre-study intervention)	•	•									Sections 8.3.1 and 10.3.8
Subsequent pregnancies							•	•	•	•	
Record interest in joining future extension study								•			Section 6.6

CONFIDENTIAL

214725 (RSV MAT-012)
Protocol Amendment 1 Final

Visit / Contact	Screening	V1	C1	V2 ¹	Monthly contacts until delivery ⁶	V3	V4	C2	Safety Visit - Event-driven	RSV-associated MA-RTI Visit - Event-driven ⁷	Notes
Timepoint	D (-28) – D 1	D1 (24 ^{0/7} - 36 ^{0/7} weeks of gestation)	D8	D31		Delivery	D43 Post-delivery	D181 Post-delivery			For monthly contacts: Section 8.4.2.1 Additional contacts and/or visits can be made between Visit-2 and the Delivery visit if deemed necessary.
Screening conclusion	●										
Study conclusion								●			Sections 4.4 and 10.1.9

V = visit; **C** = Contact; **D** = day; **MA-RTI** = medically attended respiratory tract illness; **LAR** = Legally acceptable representative

● is used to indicate a study procedure that requires documentation in the individual eCRF.

○ is used to indicate a study procedure that does not require documentation in the individual eCRF.

¹ Visit 2 (Day 31) may be replaced by Visit 3 (Delivery) in case of premature delivery. If the delivery date occurs prior to Day 31 post-study intervention, there will be no Visit 2 (Day 31).

² Fever is defined as temperature ≥38.0°C/100.4°F regardless of the location of measurement. The preferred location for measuring temperature in this study is the oral cavity.

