8.1.1. Biological samples (Amended 15 March 2022)

Table 10 Biological samples - Maternal participants (Amended 15 March 2022)

Maternal Sample type	Collected to evaluate	Minimum Quantity per participant	Unit	Time point	Additional information
Whole blood	Hematology, Biochemistry	~5.5	mL	Screening	Blood sample to be collected and analyzed locally only if not performed as per standard of care. ⁵
	Immune response ¹	~10	mL	Visit 1 (Day 1) pre-Dose	-
				Visit 2 (Day 31) ⁴	
Visit 3 (Delivery)					
Urine	Protein, Glucose	Dipstick	NA	Screening	Urine sample to be collected and analyzed locally only if not performed as per standard of care. ⁵
Nasal Swab ^{2, 3, 6}	Presence of RSV-A/B	-	-	MA-RTI Visit (Event-Driven)	Collect a nasal swab from any maternal participant who reports a MA-RTI.
				RTI hospitalization (Event-Driven)	Collect a nasal swab (if possible) from any participant hospitalized with RTI (or soon after discharge, as long as symptoms are ongoing).

¹ Volume of the blood sample collected for immune response assessment may be reduced to ~5 ml at investigator’s discretion. Refer to the laboratory manual for additional information.

² Collection of a nasal swab for sponsor testing is additional to and **DOES NOT REPLACE** any specimen collection (per local standard of care) for **testing by the local laboratory** to establish a fast and accurate diagnosis for the hospitalization. In the case of hospitalization, local testing for RSV infection should be performed if feasible.

³ If other nasal swab specimens are collected and tested locally as per local standard of care, results will be recorded in the eCRF. In principle only the sponsor laboratory results will be used when applying the case definitions for data analysis in Section 4.2.5.3. Thus, **where mandated by the protocol, every effort should be made to obtain nasal swab samples that can be analyzed by the sponsor (or sponsor-designated) laboratory.** Results of locally tested samples, with locally approved tests may be used when applying case definitions only in the event the nasal swab for central testing was impossible to collect.

⁴ Blood sample at Visit 2 (Day 31) will not be collected if the delivery occurs prior to Day 31 post-study intervention.

⁵ Blood sample for hematology, biochemistry evaluation should be tested and analyzed locally.

⁶ **Due to the change in the study requirements, nasal swab samples will no longer be collected from any maternal participant for RTI assessment.**

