8.3.2. Method of detecting AEs and SAEs, pregnancies and other events

Detection and recording of AE/SAE/AESI/subsequent pregnancies are detailed in Section 10.3.8.

Assessment of AE/SAE intensity, causality and outcome are described in Section 10.3.9.

Open-ended and non-leading verbal questioning of participants/participants' parent(s)/LAR(s) is the preferred method of acquiring information related to an AE/SAE/AESI/ subsequent pregnancy.

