**** Due to the stop on RTI surveillance for maternal participants, these checks will no longer be performed.***

For infant participants:

- Temperature
- Respiratory rate
- Blood oxygen saturation measured by pulse oximetry (Section 8.2.1.4.1), in room air, if feasible
- Results of chest auscultation
- Presence of cough, runny nose or blocked nose

- Signs of difficulty in breathing (wheezing, tachypnoea, nasal flaring, chest in-drawing and apnea)
- Irritability/agitation
- Lethargy/excessive sleepiness
- Cyanosis
- Feeding poorly

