1.2. Study Design

Overview of Study Design and Key Features

Figure 1 and Figure 2 provide overviews of the study design for maternal and infant participants, respectively.

Figure 1 Study design overview – Maternal participants

MAE = medically attended adverse event; **MA-RTI** = medically attended respiratory tract illness; **(S)AE** = (serious) adverse event; **SCR** = screening

¹ Visit 2 (Day 31) may be replaced by Visit 3 (Delivery) in case of premature delivery. If the delivery date occurs prior to Day 31 post-study intervention, there will be no Visit 2 (Day 31).

² SAEs related to study participation are to be collected from screening to Visit 1 (Day 1 pre-study intervention).

³ Following study intervention (RSV maternal vaccine or placebo) administration, SAEs and (S)AEs leading to study withdrawal are to be collected from Day 1 (Visit 1) up to 180 days post-delivery (Contact 2).

⁴ If not performed as part of the routine care, the blood and urine samples for screening should be collected within 15 days prior to study intervention administration.

⁵ **Due to the recent safety signal in RSV-MAT-009, there will be no further enrollment and vaccination of maternal participants. Refer to Protocol section 2.3 for further details.**

[figure not shown]
⁶ **Due to the change in the study requirements, MA-RTIs experienced by the maternal participants will no longer be collected.**

⁷ **In addition to the monthly contacts between Visit-2 and the Delivery visit, additional not pre-specified contacts and/or visits can be made more often (at any desired frequency), as per investigator's, maternal participant's or LAR's discretion.**

Note: Placenta samples will be collected at delivery from all maternal participants, whenever feasible. These samples may be tested to support possible safety assessments, if necessary. Additional details are provided in the study procedures manual (SPM).

Overview of Study Design and Key Features

Figure 2 Study design overview – Infant participants

AESI = adverse event of special interest; **MAE** = medically attended adverse event; **RTI** = respiratory tract illness; **(S)AE** = (serious) adverse event

Infant sub-cohorts are abbreviated “BS1”, “BS2” and “BS3” correspond to Visit 2-NB (Day 43 post-birth), Visit 3-NB (Day 121 post-birth) and Visit 4-NB (Day 181 post-birth), respectively.

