4.1.2.3. RSV infection

The sponsor will analyse nasal swabs by quantitative reverse transcription polymerase chain reaction (qRT-PCR) for the presence of RSV-A/B. A positive (RSV-A or B) test result constitutes a case of RSV infection. Refer to Table 10, Table 12 and section 8.4 of the Protocol.

In the event the collection of a nasal swab for testing by the sponsor is impossible, results from locally collected samples, tested with locally approved tests, may also be considered for the determination of a case of RSV infection.

Note: Due to the change in the study requirements, RTI surveillance of the maternal participants will no longer be performed.

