4.1.2.4. RTI and LRTI

RTI cases will be classified (during data analyses) according to the definitions provided in [Table 9*](#) and [Table 10](#).

**** Due to the change in the study requirements, RTI surveillance of the maternal participants will no longer be performed.***

Table 9 MA-RTI case definitions for data analysis in maternal participants

RSV-MA-RTI	Medically attended visit for RTI symptoms AND Confirmed RSV infection ^{1,2}
RSV hospitalization	Confirmed RSV infection AND Hospitalized for acute medical condition ³
All-cause MA- RTI	Medically attended visit for RTI symptoms

¹ Confirmed RSV infection defined in Section 4.2.5.3 of the Protocol

² RSV (nasal swab) sampling and testing as specified in Table 10 of the Protocol.

³ Hospitalization is defined as admission for observation or treatment based on the judgment of a health care provider.

MA-RTI = Maternal, medically attended respiratory tract illness

Note: Due to the change in the study requirements, RTI surveillance of the maternal participants will no longer be performed.

Table 10 RTI/LRTI case definitions for data analysis in infants

RSV-RTI	Runny nose, OR Blocked nose, OR Cough AND Confirmed RSV infection ⁴
RSV-LRTI	History of cough OR difficulty in breathing ¹ AND SpO ₂ < 95% ² , OR RR increase ³ AND Confirmed RSV infection ⁴
RSV-severe LRTI	Meeting the case definition of RSV-LRTI AND SpO ₂ < 93% ² , OR lower chest wall in-drawing, OR inability to feed, OR failure to respond / unconscious
RSV hospitalization	Confirmed RSV infection ⁵ AND Hospitalized for acute medical condition ⁶
All-cause RTI	Runny nose, OR Blocked nose, OR Cough
All-cause LRTI	History of cough OR difficulty in breathing ¹ AND SpO ₂ < 95% ² , OR RR increase ³
All-cause LRTI hospitalization	Hospitalized due to all-cause LRTI as defined above

Definitions are modified from [Modjarrad, 2016]; **RTI** = respiratory tract illness; **LRTI** = lower respiratory tract illness; **RR** = respiratory rate; **SpO₂** = blood oxygen saturation by pulse oximetry.

¹ Based on history reported by parents/LARs and includes difficulty in breathing (e.g. showing signs of wheezing or stridor, tachypnoea, flaring [of nostrils], chest in-drawing, apnea).

² For blood oxygen saturation (SpO₂), the lowest value monitored will be used. In high altitudes (>2500m), SpO₂ <92% for LRTI, <90% for severe LRTI.

³ RR increase defined as:

- > 60/minute (< 2 months of age)
- > 50/minute (2 to < 12 months of age)

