4.3. Secondary Endpoint(s) Analyses

4.3.1. Safety

4.3.1.1. Analysis of safety and reactogenicity planned in the protocol

Safety analyses in maternal participants will include summaries by study group and age category (<18 years; ≥ 18 years; overall) of solicited administration site and systemic events, unsolicited AEs, MAEs, SAEs, MA-RTIs, RSV-associated MA-RTIs, (S)AEs leading to study withdrawal, worsening of pre-existing medical conditions and/or obstetric complications, pregnancy outcomes and pregnancy-related AESIs.

Safety analyses in infant participants will include summaries by study group and gestational age at birth (≥ 37 weeks; <37 weeks; overall) of neonatal AESIs, MAEs, SAEs, (S)AEs leading to study withdrawal, and occurrence of RSV- associated LRTIs, severe LRTIs, RSV-associated hospitalization.

CONFIDENTIAL

The reactogenicity analysis will be performed on Solicited Safety Set for maternal participants, and other safety analyses will be performed on the Exposed Sets for both maternal and infant participants.

	Secondary Safety Endpoints	Statistical Analysis Methods
Maternal participants	Number and percentage of maternal participants reporting SAEs, (S)AEs leading to study withdrawal and MAEs from Day 1 up to 180 days post-delivery.	The number and percentage of maternal participants reporting: 
 at least one SAE at least one (S)AE leading to study withdrawal at least one MAE from Day 1 up to 180 days post-delivery with exact 95% CIs will be tabulated by group and by MedDRA preferred term. By participant listings of SAEs, (S)AEs leading to study withdrawal and MAEs will be prepared.
	Number and percentage of maternal participants reporting worsening of pre-existing medical conditions and/or obstetric complications from Day 1 up to 180 days post-delivery.	The number and percentage of maternal participants reporting each worsening of pre-existing medical conditions and/or obstetric complications from Day 1 up to 180 days post-delivery will be tabulated with its exact 95% CI by group. By participant listings of worsening of pre-existing medical conditions and/or obstetric complications will be prepared.
	Number and percentage of maternal participants reporting RSV-associated MA-RTIs from Day 1 up to 180 days post-delivery.	The number and proportion of participants reporting at least one RSV-associated MA-RTI from Day 1 up to 180 days post-delivery with exact 95% CIs will be calculated and tabulated.

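### Maternal RTI surveillance and sponsor swabs were stopped, but the SAP still reports RSV-associated MA-RTI to 180 days post-delivery over all dosed women, so the proportion is biased low where the window was still open

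*SAP*

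**What the plan says.** **The endpoint.** For maternal participants, SAP 4.3.1.1 tabulates "The number and proportion of participants reporting at least one RSV-associated MA-RTI from Day 1 up to 180 days post-delivery with exact 95% CIs". SAP Table 1 gives the same window. SAP 4.3.1.2.5 places the RTI analyses on the Exposed Set, which SAP Table 3 defines as all women who were dosed. SAP 4.6.2 repeats the endpoint by age category. The opening paragraphs of SAP 4.2.1.1 and 4.3.1.1 also list all-cause MA-RTIs.

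**The stop.** SAP 1.2 (Figure 1 footnote) states: "Due to the change in the study requirements, MA-RTIs experienced by the maternal participants will no longer be collected". Protocol 8.1.1 (Table 10 footnote) adds that "nasal swab samples will no longer be collected from any maternal participant for RTI assessment". Protocol 8.4.4.1 says of the maternal clinical assessments: "Due to the stop on RTI surveillance for maternal participants, these checks will no longer be performed".

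**What remains.** Protocol Table 1 keeps a row for "SAEs, (S)AEs leading to study withdrawal, MAEs (Day 1 post-study intervention to 180 days post-delivery". Protocol 8.3.2 prefers "Open-ended and non-leading verbal questioning of participants" as the way to learn of events. Protocol 8.3.1 still counts RTI hospitalizations as SAEs, and Table 10 asks for local RSV testing on hospitalization if feasible.

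**What a case needs.** SAP Table 9 defines RSV-MA-RTI as "Medically attended visit for RTI symptoms AND Confirmed RSV infection". When a sponsor swab cannot be obtained, SAP 4.1.2.3 allows that "results from locally collected samples, tested with locally approved tests, may also be considered for the determination of a case of RSV infection".

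**What is absent.** Neither the missing-data rules (SAP 6.2.3) nor the changes to protocol-defined analyses (SAP 4.8) truncates, censors or restricts this endpoint.

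**The concern.** A case needs two things: a medically attended visit that comes to the site's notice, and confirmation of RSV. The stop weakens both. Before it, sites made scripted monthly contacts, women were told to report respiratory visits themselves (Protocol 8.4.2.1), and the sponsor tested swabs by PCR. Afterwards, general adverse-event enquiry and whatever local testing takes place are left. The numerator can lose cases, while the denominator and the window stay as they were. Time that was hardly observed is counted as event-free.

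The study tests no hypotheses, so the reported proportion and its interval are themselves the result. A percentage labelled as running to 180 days post-delivery would be read as a risk over that period. The exact interval would reflect sampling error only and nothing of the lost surveillance.

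**Working it through.** The plan states no expected rate or precision for maternal RSV-associated MA-RTI, so there is no figure on this endpoint to reproduce. The nearest one is the zero-event limit in SAP Table 13, reproduced in step 4.

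**1. Who had an open window.** The window runs from dosing to 180 days after delivery.
- Shortest possible window: 180 days (delivery on the day of dosing). This is only a floor, because Protocol 5.2.1.1 excludes women likely to deliver within 7 days.
- 15 March 2022 (amendment date) − 180 days = 16 September 2021. Any woman dosed later than that and still in follow-up had an open window on the amendment date, whenever she delivered.
- Longest window used: dosing at 24 weeks and delivery at 40 weeks (assumed) gives (40 − 24) × 7 + 180 = 292 days. On that basis a window could be open on 15 March 2022 for dosing as far back as 27 May 2021.
- Protocol 10.1.1 generally requires ethics approval before a substantial amendment is implemented, so the real stop date varies by site and may be later than 15 March 2022. The documents give no site dates.

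**2. Share of the window under surveillance.** Share = days from dosing to the stop ÷ window length, for windows of 292 and 180 days.

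| Dosed | Stop 15 Mar 2022 | Stop 1 Jun 2022 (illustration) |
|---|---|---|
| 1 Dec 2021 (illustration) | 104/292 to 104/180 = 36% to 58% | 182/292 = 62%, up to 100% |
| 25 Feb 2022 (latest possible) | 18/292 to 18/180 = 6% to 10% | 96/292 to 96/180 = 33% to 53% |

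The second row is an extreme bound. Protocol 2.3 describes a pause in vaccination, with no start date given, before the stop on 25 February 2022, so the last dose may have been earlier. The date 1 June 2022 is that of the SAP amendment and is not evidence of any site's stop.

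**3. Illustrative shortfall.** Let r be the true full-window risk, s the group-average share surveilled, and c the share of later cases still confirmed. Under a constant hazard, the expected reported proportion is 1 − (1 − r)^(s + c(1 − s)).

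| r | c | s = 75% | s = 50% |
|---|---|---|---|
| 1% | 0 | 0.75% | 0.50% |
| 1% | 50% | 0.88% | 0.75% |
| 5% | 0 | 3.8% | 2.5% |
| 5% | 50% | 4.4% | 3.8% |

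The relative shortfall is close to (1 − s)(1 − c): 25% or 50% with c = 0, and 12% or 25% with c = 50%. All of r, s and c are assumed.

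**4. Illustrative effect on the interval.** With zero events in 252 women (planned, not actual), the exact upper limit is 1 − 0.025^(1/252) = 1.45%, which agrees with the 1.5% in SAP Table 13. If only a share s of the window was surveilled and nothing was captured later, the Poisson limit per full window is −ln(0.025)/(252 × s). This is 1.95 per 100 windows for s = 75% and 2.93 for s = 50%. As risks, 1 − exp(−0.0195) = 1.9% and 1 − exp(−0.0293) = 2.9%.

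**The case against.** The strongest reply is that this is a reporting caveat on a descriptive secondary endpoint. The SAP discloses the stop in several places, including under the case-definition table to which its RTI section points. The endpoint matches Protocol 9.4.4.1, and the protocol keeps all planned objectives, so the silence of SAP 4.8, which records departures from the protocol, is not an error in itself. Capture also continues: MAEs and SAEs are collected to 180 days post-delivery, RTI hospitalizations remain SAEs with local RSV testing if feasible, and Protocol Table 18 still gives a reporting time for maternal MA-RTIs. Finally, replacing a percentage with a rate changes the summary measure after unblinding.

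Much of this stands. A reader might infer that ascertainment fell to zero; the documents show only that it fell, and hospitalized cases keep both a reporting and a testing route. The notes nevertheless change no analysis. Local testing is not systematic, local results are optional evidence, and the SAP does not say whether a swab stopped by design counts as one that was impossible to collect. The timing objection is met by adding the rate openly, while allowing the protocol's number and percentage to remain with a footnote.

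**Conclusion.** The point holds. In each group, the planned proportion is biased low for women whose window was open when their site stopped surveillance, and the exact interval treats the whole window as observed. The direction rests on reduced detection and confirmation with an unchanged denominator. The size cannot be computed, because the number dosed, dosing dates, site stop dates and maternal RSV risk are not given. If the risk is near zero, so is the absolute bias.

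Three stronger readings are not supported:
- **A biased comparison of vaccine with placebo.** The stop applied to both groups, and nothing in the documents shows unequal loss.
- **Women with only 6% to 10% of their window surveilled.** That needs dosing on 25 February 2022 and an immediate stop on 15 March. The documents establish neither.
- **A shortfall equal to the unsurveilled share of time.** This needs a constant hazard and no later capture. Protocol 8.4.2.2.1 itself provides for seasonal RSV transmission, so the share of time lost need not be the share of cases lost.

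The primary objectives are untouched. The correction is worth making because it is cheap and prevents a mislabelled result.

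**What to change.** Change the SAP only.

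- **4.3.1.2.5:** for maternal RSV-associated MA-RTI, and for the all-cause MA-RTI summaries in 4.2.1.1 and 4.3.1.1, end follow-up at the site's maternal surveillance stop date, or at 180 days post-delivery, withdrawal, death or loss to follow-up if earlier. Do not end it at the last surveillance contact, because women were told to self-report between contacts.
- **4.3.1.1 and 4.2.1.1:** report by group the women with a first event, the person-time to first event or end of follow-up, and the rate with an exact Poisson interval. Label it as covering the surveilled period, and give the number of women with a complete surveilled window.
- **Full-window number and percentage, if still tabulated:** footnote that surveillance stopped under Amendment 1, and do not present it as a 180-day post-delivery risk.
- **Later locally confirmed cases:** list them separately so that they stay visible.
- **4.6.2 and Table 1:** apply the same rule to the age-category summaries, and add a note to the table.
- **4.8:** record the change and that it was made after unblinding.

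The cost is SAP wording and one surveillance stop date per site, which the documents do not say is recorded. No protocol amendment is needed. The downsides are lower precision, a rate tied to the calendar period observed, early enrollees making up the women with complete windows, and a summary measure added after unblinding.

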4.3.1.2. Additional considerations

4.3.1.2.1. Analysis of solicited events

The analysis of solicited events will be performed on Solicited Safety Set. The intensity of the solicited events will be assessed as described:

Table 11 Intensity scales for solicited events in adults

Adults			
Event	Intensity grade	Parameter	
Solicited administration site events	Pain at administration site	0	None
		1	Mild: Any pain neither interfering with nor preventing normal everyday activities.
		2	Moderate: Painful when limb is moved and interferes with every day activities.
		3	Severe: Significant pain at rest. Prevents normal every day activities.
	Redness at administration site	Greatest surface diameter in mm	
Swelling at administration site	Greatest surface diameter in mm		
Solicited systemic events	Temperature*		Record temperature in °C/°F with 1 decimal Temperature will be analyzed in 0.5°C increments from ≥ 38.0°C /100.4°F) Grade 3 fever is defined as > 39.0°C /102.2°F
	Headache		
	Fatigue	0	Normal
	Nausea	1	Mild: Easily tolerated
	Vomiting	2	Moderate: Interferes with normal activity
	Diarrhea	3	Severe: Prevents normal activity
	Abdominal pain		

* Refer to Section 1.3 of the Protocol for the definition of fever and the preferred location for temperature measurement.

The maximum intensity of solicited administration site redness/swelling will be scored at GSK Biological as follows:

0	:	≤ 20 mm
1	:	> 20 mm to ≤ 50 mm
2	:	> 50 mm to ≤ 100 mm
3	:	> 100 mm

Duration in days of solicited administration site and systemic events within 7 days after study intervention will be tabulated by study group and overall, and if needed by age group. The derivation rule of duration in days for solicited events is detailed in section [6.2.4.9](#).

